Within the COVID period there were various periods of scaling up and down surgical capacity for elective hip operations, caused by external factors. For example, patient A, scheduled for surgery on Tuesday, proceeded, while patient B, scheduled for Thursday, had to be rescheduled due to changed government or regional policy effective the next day. Patient C had surgery while patient D was cancelled because the surgeon suddenly had to quarantine due to a child or partner with a COVID infection. These issues caused that in some patients THA could be performed and in other patients THA was cancelled.

We assume that whether or not such surgeries took place during the COVID period was beyond the control of patients, doctors and researchers and can be seen as a form of (pseudo)randomization. In a traditional RCT, randomization is done by means of computerized random sequence generation. In an emulation trial (1, 11), randomization is introduced by factors outside of our control, in this case whether THA surgery was cancelled or not due to the COVID-19 pandemic and the resulting scarcity of operating rooms for THA surgery.

An important step in RCT emulation is to verify the validity of the assumption that a comparison between two groups (in our study patients who did and who did not undergo THA surgery within the COVID period) is indeed (pseudo)random and requires analysis. The answer to this question is an outcome of the research, not something we can determine with certainty in advance.

Therefore, the aim of this study is to measure if THA is effective in restoring physical function in patients with osteoarthritis of the hip compared to non-surgery in existing Value-Based Health Care (VBHC) data by means of RCT Target Trial Emulation.

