3. METHODS

3.1 Study design

Hip osteoarthritis patients eligible for THA and placed on the waiting list for surgery will be included when the preoperative intake questionnaire is completed between 1-4-2020 and 1-1-2022. In a retrospective dataset we compare two standard care strategies: THA and wait-and-see, in which patients did not receive THA and remain on the waiting list. Patients were assigned to one of the two groups based on

whether surgery could be performed or whether THA was cancelled and patients remained on the waiting list. The first group (THA group) consists of patients that received surgery before 1-1-2022 and completed a 3-months postoperative questionnaire before 1-4-2022. The second group (control group) consists of patients which did not receive surgery before 1-1-2022 and completed a waiting list questionnaire before 1-4-2022. The target trial and emulation plan are shown in Figure 1 and the time-schedule of the emulation trial is shown in Figure 2. Patients that received THA on both sides between 1-4-2020 and 1-1-2022 will be excluded. The response rates on follow-up questionnaires will be reported for both groups. We will compare characteristics (age, sex, PROM-outcomes at baseline and physical therapy before the hospital visit) for patients that completed the follow-up questionnaires (completers) and patients that did not complete the follow-up questionnaires (non-completers). In the primary analysis we will correct for patient characteristics.

Target trial → Emulation

[figure not shown]
[figure not shown]

Figure 2: Timeline target trial emulation

THA= Total Hip Arthroplasty

FU = Follow-up

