In this study we compare the effect of THA compared to non-surgery on hip disability measured with the HOOS-PS change score from baseline up to approximately 3-months by means of RCT Target Trial Emulation, which aims to mimic a traditional RCT. Function and pain as a secondary outcome are measured by means of patient reported outcome measures (PROMs) pre-operatively and post-operatively or post-waiting list. The pre-operative intake questionnaire and the 3-months postoperative questionnaire are part of standard care. The waiting list questionnaire was administered during the Covid-19 pandemic to monitor patients' health status in two Santeon Hospitals (OLVG and Martini) in all patients who were at least three months on the waiting list. Therefore our study will be performed with data of these two Santeon Hospitals. All data is available through the routinely collected data for hip osteoarthritis within the VBHC program and in addition the outcomes of the administered waiting list questionnaire. Therefore, it is not needed to obtain additional information from patients.

To test the assumption that group allocation is (pseudo)random and cannot be explained by patient characteristics or severity of pain and hip disability at baseline, a logistic regression analysis will be performed on patients within the VBHC data set between 1-4-2020 and 1-1-2022. Group being the dependent variable (THA vs. non-surgery) and age (continuous), sex (M/F), physical therapy before the hospital visit (yes/no), follow-up time in days (continuous), pain at baseline (NRS, continuous) and the HOOS-PS at baseline (continuous) will be included in the model as independent variables. Secondly, we will test the assumption that follow-up time in days is not statistically significantly different between the THA and non-surgery group. Follow-up time is defined by calculating the number of days between the date of the orthopedic visit) and the date of the follow-up questionnaire. Results will be considered statistically significant when $p \leq 0.05$. In case an independent variable has a statistically significant effect on group assignment and/or follow-up time in days is significantly different between the two groups, clinical relevance will be considered and discussed within the research team, for example the effect size on chance to be allocated to the THA or non-surgery group.

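### As specified, the allocation check can use only patients who returned a follow-up form, so it tests allocation mixed with response

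*Combined protocol and SAP*

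**What the plan says.** Section 3.1 gives the purpose of the check: "To test the assumption that group allocation is (pseudo)random and cannot be explained by patient characteristics or severity of pain and hip disability at baseline". For this, "a logistic regression analysis will be performed on patients within the VBHC data set between 1-4-2020 and 1-1-2022". The outcome is group (THA or non-surgery). The regressors are age, sex, prior physical therapy, baseline pain, baseline HOOS-PS and follow-up time in days. Section 1.4.2, item 2, repeats the model. On the last regressor: "Follow-up time is defined by calculating the number of days between the date of the orthopedic visit) and the date of the follow-up questionnaire".

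Section 3.1 describes the THA group as "patients that received surgery before 1-1-2022 and completed a 3-months postoperative questionnaire before 1-4-2022", and the control group as patients who "did not receive surgery before 1-1-2022 and completed a waiting list questionnaire before 1-4-2022". The same section also assigns patients by whether surgery went ahead or was cancelled, and promises response rates for both groups. It adds: "We will compare characteristics (age, sex, PROM-outcomes at baseline and physical therapy before the hospital visit) for patients that completed the follow-up questionnaires (completers" and those who did not. It does not say whether that comparison is made within group.

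On whether allocation was pseudo-random, the Introduction says: "The answer to this question is an outcome of the research". The end of section 3.1 makes the causal reading depend on it.

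**The concern.** The natural experiment is that surgery was performed or cancelled for reasons unrelated to the patient. That event involves every listed patient with an intake form, and it comes before anyone answers a follow-up form. A check fitted only in responders sees the joint result of two processes: who was operated on, and who then replied. The two can offset each other or add.

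There is a reason to expect response to differ by group. One form is the routine 3-month postoperative questionnaire. The other was a pandemic questionnaire sent in two hospitals to patients at least three months on the list. Patients answered one after surgery and the other while still waiting.

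At stake is the evidence for the pseudo-randomisation claim. A clean result in responders would not by itself show clean allocation, and a flagged result would not by itself show that allocation failed.

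**Working it through.** **Who can enter the model.** A patient without a follow-up form has no follow-up date, hence no value for follow-up days. The plan describes no imputation, so a standard logistic fit drops that patient. The group descriptions in 3.1, read literally, also leave such a patient without a group. On either ground the fitted sample is responders only, although the population named in the text is wider.

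**How much this could matter.** The plan has no figure to reproduce: it gives no sample size calculation, power or response rate. The only size given is at least 100 patients per group (1.2.2). Everything else here is assumed:

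- 320 listed patients, half operated, about 62% response, so about 160 listed and 100 responders per group.
- Allocation log-odds ratio 0.35 per SD of baseline severity (sicker patients operated on more often), giving a mean difference *d* of about 0.34 SD, or 0 for random allocation.
- Response log-odds slopes *b*T (after THA) and *b*C (on the list) per SD of severity.
- A two-sided test at 0.05 on one severity variable.

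With mean response *p*, a slope *b* shifts mean severity among responders by about *b*(1 − *p*). For *b* = 0.4 this is 0.4 × 0.38 = 0.15 SD. So among responders *d*R ≈ *d* + (*b*T − *b*C)(1 − *p*). With *z* = |*d*R|√(*n*/2), the chance of a flag is about Φ(*z* − 1.96) + Φ(−*z* − 1.96).

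| Sample and response pattern (*b*T / *b*C) | *d*R | *z* | Formula | Simulated |
|---|---|---|---|---|
| Biased, all listed (*n* = 160) | 0.34 | 3.04 | 86% | 87% |
| Biased, responders (*n* = 100), 0 / 0 | 0.34 | 2.40 | 67% | 67% |
| Biased, responders, 0 / +0.4 | 0.34 − 0.15 = 0.19 | 1.34 | 27% | 27% |
| Biased, responders, −0.4 / +0.4 | 0.34 − 0.30 = 0.04 | 0.28 | 6% | 6% |
| Random, responders, 0 / 0 | 0 | 0 | 5% | 5% |
| Random, responders, 0 / +0.4 | −0.15 | 1.06 | 19% | 18% |
| Random, responders, −0.4 / +0.4 | −0.30 | 2.12 | 56% | about 55% |

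The fall from 87% to 67% is lost sample size; only the further fall is response selection. With equal slopes of 0.4 in both groups, *d*R is essentially unchanged: simulation gives 65–66% under biased allocation and 5% under random allocation. With slopes reversed (+0.2 / −0.2), *d*R is about 0.34 + 0.15 = 0.49 and biased allocation is flagged in about 93%, more often than in all listed patients.

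**Cross-check with a multivariable logistic model.** A separate simulation assumed 400 listed patients, about 50% response and an allocation odds ratio of 0.67 per SD. Baseline HOOS-PS was flagged in 92–94% of runs in all listed patients. In responders it was flagged in 68% with no selective response, 24% with a response odds ratio of 1.5 after THA only, and about 5% with opposite response odds ratios of 1.5 and 1/1.5. Under random allocation, an odds ratio of 1.5 in controls only gave 22%, and opposite odds ratios gave 68%. At 70% response the opposite patterns gave 20% (biased) and 34% (random). Adding follow-up days with the same distribution in both groups changed these figures by less than one point. The damage therefore comes from the patients dropped, not from the extra coefficient.

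**The existing safeguard.** If the completer comparison is pooled over groups, it flags severity in about 5% of runs under the opposite-slope patterns, which is chance level. With a slope of 0.4 in one group only it flags about 40%. It is therefore a partial safeguard unless made within group.

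**The case against.** A reader might infer that group itself requires a returned form, so that dropping follow-up days would cure nothing. The documents do not settle that. Section 3.1 also assigns patients by whether surgery could be performed, and response rates for both groups are possible only if non-responders have a group. On that reading follow-up days is the only obstacle. The check as specified loses the non-responders either way.

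A reader might also take 6% and 55% as the expected performance. They are adverse cases that need opposite-sign response slopes, for which the documents offer no evidence. With equal slopes there is no distortion beyond lost power.

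A third tempting inference is that the treatment effect is biased. This point does not show that. The primary model in 1.4.2 adjusts for baseline HOOS-PS, pain, age, sex and physical therapy. In a simulation with a linear outcome the adjusted effect stayed at −1.49 to −1.50 against a true −1.50 in every pattern. What remains is that adjustment covers measured factors only, whereas the pseudo-randomisation claim is meant to reach unmeasured ones as well.

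Two further points for the plan stand. A flag leads to a discussion of clinical relevance, not to an automatic failure. And imbalance among responders is real imbalance in the sample analysed, so that fit should be kept.

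Nor would a fit in all listed patients be clean by itself. Patients listed late can be unoperated through timing without any cancellation, and some waiting patients may never have been sent the form.

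**Conclusion.** The concern holds in a limited form. As specified, the check drops all non-responders and tests allocation mixed with response, while the assumption concerns whether surgery was performed or cancelled. It can mislead in either direction, but only if response depends on baseline severity differently in the two groups. In the assumed setting, a slope of 0.4 in one group lowers detection of a biased allocation in responders from 67% to about 27%, and raises false flags under random allocation from 5% to about 18%. The actual size is unknown because no response rates are given. The documents do not show that allocation was biased, or that the primary estimate is. The weakness is in the diagnostic on which the causal reading rests.

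**What to change.** For the check:

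1. Define group by surgery status and remove follow-up days from the model. The separate comparison of follow-up time between groups can stay.
2. Fit age, sex, physical therapy, baseline pain and baseline HOOS-PS in all listed patients with an intake form, whether or not a follow-up form came back.
3. Account for listing date: include the THA order date, or restrict to patients listed long enough to have been eligible for the waiting-list form.
4. Repeat the fit in the analysed responders and report both. Use the first to judge allocation and the second to describe balance in the analysed sample. Do not read the gap between them as response alone.
5. Make the completer versus non-completer comparison within each group, separating patients never sent a form from those who did not return it where the data allow.

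The cost is a wording change and one or two extra logistic runs. Order date, surgery date, intake scores and covariates are already in the variable table (1.3.2), so no new data are needed.

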We hypothesize that patient characteristics (i.e. sex, age, severity of symptoms at baseline) do not affect group allocation and follow-up time is similar for THA and non-surgery patients. If this is true, the proposed Target Trial Emulation will provide the first evidence on the effectiveness of THA surgery in terms of causal inference.

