1.2 Recruitment and selection of subjects

1.2.1 Screening/selection

Retrospective data will be collected by [name] and the VBHC data analysts at OLVG and Martini hospital.

1.2.2 Study population
 
Patients with hip osteoarthritis that were on the waiting list for THA between 1-4-2020 and 1-1-2022 and had a completed intake questionnaire will be included. The number of patients is dependent on how many patients completed the questionnaires and needs to be investigated. However, based on the waiting list at the time and the number of performed surgeries in the two hospitals, we expect to include at least 100 patients in each cohort (THA group and non-surgery group). Since we use observational data for trial emulation, no sample size calculation is needed (8).

1.2.3 Inclusion criteria
 
Inclusion criteria:
 
 - Patients on the waiting list for primary THA between 1-4-2020 up to 31-3-2022 in OLVG or Martini hospital. - Completed intake questionnaire (HOOS-PS baseline) - Indication osteoarthritis of the hip

1.2.4 Exclusion criteria
 
Exclusion criteria:
 
 - Patients that received THA on both sides within follow-up (1-4-2020 and 1-1-2022) will be excluded. - Patients with other indications than osteoarthritis of the hip were excluded.

1.2.5 Number of subjects/ sample size
 
Since we use observational data for trial emulation no sample size calculation is needed (8). The participants are already exposed to an intervention or not. Differences in the primary and secondary outcomes (PROMs) between groups will be interpreted using 95% confidence intervals and thresholds for clinical relevance which are reported below.

1.3 Data collection: variables and measurement methods
 
1.3.1 Primary outcome measure (dependent variable)
 
Primary outcome is the change score for hip function measured with the HOOS-PS at 3-months postoperative in the THA group and at least 3-months post waiting list in the control group compared to baseline. The HOOS-PS is a 5-item questionnaire that quantifies hip disability. The raw outcome is converted to a Rasch-based interval score ranging from no difficulty (0) to extreme difficulty (100) (3,4,5). The minimal clinically important difference (MCID) for the HOOS-PS is 23 points (6). We will also calculate the minimal important change in our study population, based on an anchor question.

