1.4.2 Analyses

 1. Measure if THA is effective to improve physical function in patients with osteoarthritis of the hip compared to non-surgery by means of RCT Target Trial Emulation. 2. Assessment to test the assumption that group allocation to the surgery group or non-surgery group cannot be explained by patient characteristics by means of logistic regression analysis. Secondly we test the assumption that follow-up time in days is similar between the two groups. 
1. Measure effect of THA: Two multiple regression analyses will be performed with the HOOS-PS and pain change score, respectively, as the dependent variable, and experimental condition (THA/ no-THA), age, sex, HOOS-PS score at baseline, pain score at baseline, physical therapy before baseline (yes/no) and follow-up time in days as independent variables. All regression coefficients and their 95% confidence intervals will be provided. Differences will be considered statistically significant when $p \leq 0.05$ and clinically relevant when differences exceed the MCID of 23 points for the HOOS-PS and 2 points for the NRS (6,7).
 
Descriptives on all independent variables will be presented and assessed by visual inspection of boxplots (for continuous variables) or tables (for categorical variables). These results will be provided for transparency purposes.
 
2. Test whether assumptions for target trial emulation are met. A logistic regression analysis will be performed on patients within the VBHC data set between 1-4-2020 and 1-1-2022 to check whether the group allocation cannot be explained by patient characteristics. Group being the dependent variable (THA vs. non-surgery) and age (continuous), sex (M/F), physical therapy before the hospital visit (yes/no), follow-up time in days (continuous), pain at baseline (NRS, continuous) and the HOOS-PS at baseline (continuous) will be included in the model as independent variables. Results will be considered statistically significant when $p \leq 0.05$. In case an independent variable has a statistically significant effect on the outcome, clinical relevance will be considered and discussed for the effect size on chance to be allocated to the THA or non-surgery group. Secondly, we will test the assumption that follow-up time in days is not statistically significantly different between the THA and non-surgery group. Follow-up time is defined by calculating the number of days between the date of the orthopedic visit) and the date of the follow-up questionnaire.

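### The allocation check reads baseline HOOS-PS and baseline pain only as mutually adjusted coefficients, so a similar-sized imbalance in both can go unflagged

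*Combined protocol and SAP*

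**What the plan says.** Section 3.1 sets out to test whether "group allocation is (pseudo)random and cannot be explained by patient characteristics or severity of pain and hip disability at baseline". The tool is one logistic regression of group on age, sex, prior physical therapy, follow-up days, baseline weight-bearing pain and baseline HOOS-PS, all entered together: "pain at baseline (NRS, continuous) and the HOOS-PS at baseline (continuous) will be included in the model as independent variables". The significance level is 0.05.

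The trigger is stated per variable: "In case an independent variable has a statistically significant effect on group assignment and/or follow-up time in days is significantly different between the two groups", the research team will consider and discuss clinical relevance, for example the effect size on the chance of allocation. Section 1.4.2, item 2, repeats this ("In case an independent variable has a statistically significant effect on the outcome"; the outcome there is group allocation).

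The only separate between-group test is for follow-up time: "Secondly, we will test the assumption that follow-up time in days is not statistically significantly different between the THA and non-surgery group". No joint test of the two severity scores is planned, and no unadjusted THA-versus-non-surgery comparison of either score. The comparison of characteristics in Section 3.1 is between completers and non-completers. Section 1.4.2 presents descriptives for visual inspection, without saying that they are by group and without a rule for judging them.

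Section 3.1 closes with the expectation being tested: "We hypothesize that patient characteristics (i.e. sex, age, severity of symptoms at baseline) do not affect group allocation". If that and similar follow-up time hold, the study is said to provide causal evidence on THA.

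**The concern.** HOOS-PS and weight-bearing pain are two patient-reported measures of the severity of the same hip disease, so a positive correlation at baseline is plausible. In a model that contains both, the part they share is credited to neither coefficient. Selection on severity could well make one group worse on both scores, and this is the pattern in which reading the coefficients one by one loses most information.

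The conclusion about (pseudo)random allocation is at stake. That conclusion also has to carry severity that was not measured, which no regression on the two recorded scores can supply. The effect-size discussion does not rescue the check, because the mutually adjusted odds ratios are themselves attenuated.

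**Working it through.** The plan gives no power figure for this check, so there is nothing of its own to reproduce.

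**Inputs from the documents.** At least 100 patients expected per group (Section 1.2.2); significance at 0.05 (Sections 3.1 and 1.4.2), taken as two-sided because sidedness is not stated; both scores in one model.

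**Assumptions not in the documents.** Standardised shifts d1 and d2 in the two scores between groups; correlation r between the scores; other covariates unrelated to group.

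**Formulas** (normal approximation, n per group).
- Unadjusted: m = d × √(n/2). For d = 0.4, m = 0.4 × √50 = 2.83, which gives power 0.81 for each score.
- Mutually adjusted: z1 = (m1 − r·m2)/√(1 − r²), and likewise for z2; the two test statistics have correlation −r. With equal shifts this is z = m × √((1 − r)/(1 + r)).
- Joint test: noncentral chi-square, 2 df, noncentrality (m1² − 2r·m1·m2 + m2²)/(1 − r²).
- Adjusted log odds ratio per SD relative to the unadjusted one, equal shifts: about 1/(1 + r).

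**Equal shifts of 0.4 SD, 100 per group.**

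| r | adjusted z | planned check flags at least one score | 2-df joint test | log odds ratio retained |
|---|---|---|---|---|
| 0.3 | 2.08 | 84% | 89% | 0.77 |
| 0.5 | 1.63 | 68% | 84% | 0.67 |
| 0.7 | 1.19 | 44% | 79% | 0.59 |
| 0.8 | 0.94 | 31% | 77% | 0.56 |

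Worked row, r = 0.5: z = 2.83 × √(0.5/1.5) = 1.63; noncentrality = 2 × 8/1.5 = 10.67.

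The planned check loses although it has two chances at 0.05. With no imbalance it flags 9.1%, 8.3% and 7.8% of studies at r = 0.5, 0.7 and 0.8, against 5% for the joint test.

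**Simulation of the full six-covariate model** (2,000 runs per setting, shifts of 0.4 SD). At r = 0.5, 0.7 and 0.8 the planned check flagged 63%, 42% and 30%, and the joint test 82%, 79% and 75%. In 18%, 38% and 48% of runs neither severity coefficient was flagged although both unadjusted t-tests were significant.

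**Unequal shifts, 100 per group.**

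| shifts (SD) | r | planned check | joint test |
|---|---|---|---|
| 0.4 / 0.3 | 0.5 | 63% | 75% |
| 0.4 / 0.3 | 0.7 | 51% | 72% |
| 0.4 / 0.2 | 0.5 | 71% | 72% |
| 0.4 / 0 | 0.5 | 91% | 84% |

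**Larger groups.** With 200 per group and shifts of 0.4 SD in both, the figures are 94% against 99% at r = 0.5, and 53% against 97% at r = 0.8.

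**The case against.** Four points stand on the other side.

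1. A reader might infer that a missed imbalance biases the treatment effect. The documents do not support this. Section 1.4.2 puts both baseline scores in both outcome models, so measured differences in them are adjusted for whether or not the check flags them.
2. A reader might infer that the check is generally blind to severity. It is not. The large deficit needs both substantial correlation and near-equal shifts. At r = 0.3 the gap is 5 points, at 0.4/0.2 SD it nearly vanishes, and when only one score shifts the planned model does better.
3. A reader might infer that non-significant coefficients formally license the causal claim. The plan makes significance a trigger for team discussion, and Section 1 calls the validity of the assumption an outcome of the research. The condition in Section 3.1 refers to the hypothesis being true, not to p-values.
4. A joint test is still a significance test. With shifts of 0.3 SD in both scores it flags 58%, 53% and 50% at r = 0.5, 0.7 and 0.8, and so misses about half. Replacing one p-value with another is not enough.

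The planned descriptives might also reveal the imbalance by eye, but they carry no rule and are not said to be by group. None of this removes the gap: no planned step states how far the two groups differ on either score before mutual adjustment.

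**Conclusion.** The point holds in a limited form. When the groups differ by a similar amount on both scores and the scores are at least moderately correlated (r of about 0.5 or more), the planned reading is clearly weaker than a joint one: 68% falling to 31% flagged, against 84% falling to 77%, for 0.4 SD in both with 100 per group. It also understates the effect sizes, retaining about 0.67 to 0.56 of the unadjusted log odds ratio per SD over r = 0.5 to 0.8.

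These figures rest on assumed shifts and an assumed correlation. The correlation can be computed from data already held. The consequence is possible false reassurance about (pseudo)random allocation, and hence about unmeasured severity, on which Section 3.1 leans for its causal claim. It is a weakness in a supporting diagnostic, worth correcting before the analysis because the correction is so cheap.

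**What to change.** In Sections 3.1 and 1.4.2 (item 2):

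- Report the unadjusted THA-versus-non-surgery difference in baseline HOOS-PS and in baseline pain, each as a standardised difference with its 95% CI, and name these as the main evidence on severity balance. With 100 per group the half-width is about 1.96 × √(2/100) = 0.28 SD, so the interval shows how much imbalance remains compatible with the data.
- Keep the logistic model and add a 2-df likelihood-ratio test that drops HOOS-PS and pain together.
- State that the two mutually adjusted p-values will not be read as the test of severity.

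The cost is one sentence in the plan, one extra model comparison and a slightly longer table. No new data are needed.
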